Eighty-four percent of pre-dose samples collected at Baseline had Trogarzo® levels below the limit of detection (<100 ng/mL). The remaining samples (16%) had detectable levels of serum Trogarzo®, generally in the range of 100 to 200 ng/mL, despite no prior treatment with Trogarzo®. As expected for pre-dose samples, all were reported to have had low receptor occupancy (<32%), as indicated previously. Although low but detectable levels of Trogarzo® may result from faulty sample collection or sample handling, it may also be due to interference with measurements of low serum Trogarzo® concentrations for specific subjects. This could confound attempts to correlate PD parameters with serum Trogarzo® concentrations in the range of 100 to 200 ng/mL, at least for certain subjects.

Serum Trogarzo® concentrations ranged from <100 to >100,000 ng/mL, collectively, for Baseline samples (pre-dose and post-dose) and pre-dose samples from Weeks 2 through 24. Comparison with receptor occupancy measurements indicated a direct relationship between serum Trogarzo® levels and CD4 receptor occupancy. A greater proportion of samples having intermediate or high receptor occupancy was evident with serum Trogarzo® concentrations  $\geq$ 150 ng/mL. At serum Trogarzo® concentrations  $>$ 300 ng/mL, over 90% of all samples were reported to have high receptor occupancy (median = 100% receptor occupancy).

In the Phase 3 study (Study TMB-301), 40 HIV-positive subjects received a 2000 mg Trogarzo® loading dose followed by 800 mg q2wk by IVI. The assay sensitivity for serum Trogarzo® concentration was 10 ng/mL. The maximum serum concentrations were observed immediately after the end of the 2000 mg Trogarzo® infusion. Steady state was reached at Week 4 after the first dose. The mean Trogarzo® concentrations were  $>$ 30  $\mu$ g/mL and the CD4 receptor occupancy was  $>$ 85% throughout the dosing period, suggesting that the regimen was sufficient to maintain the drug concentration above the therapeutic level. The loading dose effect was substantial. With the loading dose, the percentage of subjects below effective concentration and receptor occupancy decreased from  $\sim$ 50% to  $\sim$ 20% at Week 2 after the first dose by comparison between the TMB-202 and TMB-301 studies. At Week 24 after the first dose, Trogarzo® serum concentration and receptor occupancy were comparable between these two regimens.

[figure not shown]

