#### **4.5. PK**

The PK endpoints are to compare the trough serum drug concentration and AUC after IV Infusion with the diluted drug to the trough concentration and AUC after IM injection with the undiluted drug. Serum concentrations will be used to estimate PK parameters. PK parameters will be estimated for all subjects by non-compartmental analysis of the serum concentration-time data. Missing data will not be imputed. The trough concentrations and AUC for IM injection and IV infusions over 15 minutes will be

estimated. The following graphic illustrates the time points at which the  $C_{trough}$  and AUC values will be estimated.

The  $C_{trough}$  values for all IM injection and all IV infusions over 15 minutes will be estimated. A PK bridge will be demonstrated if the proportion of subjects with mean  $C_{trough}$  equal to or exceeding the threshold of 300 ng/mL are comparable for IV infusion over 15 minutes to IM injection. Both the geometric and arithmetic mean  $C_{trough}$  will be calculated and analysis results will be presented for both means. Analysis will be conducted by pooling all the  $C_{trough}$  measurements into two groups (IVI=Reference; IMTest) and dichotomizing the  $C_{trough}$  data ( $< 300$  ng/mL=1;  $\geq 300$  ng/mL=0). Fisher's exact test for comparing two independent binomial proportions will be conducted initially to test for equality of the proportions. In a subsequent test, the PK bridge will be based on relative risk assuming that the binary data in the two infusion groups are independent samples. Two one-sided tests of significance (TOST) will be carried out for the pair of hypotheses,  $H_{0a}: \rho \leq \rho_0$  versus  $H_{1a}: \rho > \rho_0$  and  $H_{0b}: \rho \geq \rho_1$  versus  $H_{1b}: \rho < \rho_1$ . Rejection of both  $H_{0a}$  and  $H_{0b}$  would mean that the relative risk lies in the zone of equivalence. The syntax below will be used in SAS to carry out the score test with  $\rho_0 = 0.8$ , and  $\rho_1 = 1.25$ .

```
proc freq data=<filename> order=data;
tables group*Cthrough/relrisk(equivalence margin=(.80, 1.25)
method=FM);
weight count;
format Cthrough Cthrough.;
run;
```

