Details of reported outputs from the analysis will be displayed in the mock tables and will include relative risk, equivalence limits, 90% confidence limits, and TOST p-values of lower margin, upper margin, and overall. Missing data will not be imputed or used in the analysis. In addition, the two-tailed p-value from Fisher's exact test will be presented to provide additional supporting evidence for equality of binomial proportions between the two administrative routes in the Ctrough cutoff at 300 ng/mL.

A 90% confidence interval of log transform of the ratio of the geometric means for IM injection to IV infusion will be calculated. Additionally, the PK bridge between the IM injection and IV infusion is demonstrated for AUC if the 90% confidence interval of log transform of the ratio of the geometric means for IM injection (test product) to IV infusion (reference product) for the 20 subjects in the study is within a 80%-125% criteria.

In accordance with the FDA Guidance (2001) [2], SAS PROC MIXED will be used to fit a factor-analytic variance-covariance structure using the FA0(2) option to the ln-transformed AUC data by subject, group (HIV+ or HIV-), PK period, and infusion type (IVI=Reference; IM=Test) to estimate 80%-125% criteria. For each type of administration, subject-level AUC data will be labeled as PK Period 1 or PK Period 2 corresponding to the graphic above. Unless a subject has missing data for both administration routes and both periods, the subject's data will be included in the analysis because SAS PROC MIXED can handle missing data. Details of reported outputs from the analysis will be displayed in the mock tables and will include mean estimate and its lower and upper bounds.

The following SAS code syntax will be used to calculate estimates:

```
proc mixed data=lnauc method=reml;
  class infusiontype population period ;
  model lnauc= population period infusiontype/ddf=kenwardroger;
  random infusiontype /type=FA0(2) subject=subject;
  repeated/group=infusiontype subject=subject;
  estimate 'T-R' infusiontype 1 -1/CL alpha=0.1;
  ods output estimates=test;
  data test;
  set test;
  meanrat= exp (estimate); * Estimated mean ratio on original scale;
  lowerb=exp(lower); * Lower bound on original scale;
  upperb=exp(upper); * Upper bound on original scale;
  proc print data=test noobs;
  var meanrat lowerb upperb;
  run;
```

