**Table 14.2.1**  
**Comparison of Geometric Mean Trough Concentrations for IM Injection to 15 Minute IV Infusions**  
**Intent-to-Treat Population**

Analysis Type	Results
Proportion of Subjects with Geometric Mean	
Ctrough $\geq$ 300 ng/ml (%)	n/NT (%)
15 Minute IV Infusion	n/NT (%)
IM Injection	xxxx
Relative Risk	(xxxx, xxxx)
90% Confidence Limits	xxxx
TOST P-values [1]	xxxx
Lower Margin	xxxx
Overall	xxxx
Upper Margin	xxxx
Fisher's exact test 2-tailed P-Value [2]	xxxx

[1] Two one-sided tests of significance (TOST) using Farrington-Manning Method and z-statistics, within an 80%-125% criteria.  
H0: P1 / P2  $\leq$  Lower Margin or  $\geq$  Upper Margin of the equivalence limits  
[2] Fishers Exact test H0: P1 is not different from P2

*Note to Programmer: SAS code provided in SAP. Any subject with at least some non-missing PK data is included*

Westat (Created on DDMMYYYY)  
S:\TMB302\DA\_IM\SAS\t\_trough1

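### The trough bridge rule puts an unexplained upper limit on a favourable proportion, so with 20 subjects a route that keeps more subjects above 300 ng/mL can seldom meet it

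*SAP*

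**What the plan says.** IM SAP 4.5 defines the trough bridge on the proportion of subjects whose mean trough reaches 300 ng/mL. Fisher's exact test is run first, but "In a subsequent test, the PK bridge will be based on relative risk", and the Fisher result is described as support: "the two-tailed p-value from Fisher's exact test will be presented to provide additional supporting evidence". The relative-risk test is coded as "relrisk(equivalence margin=(.80, 1.25", with the Farrington-Manning score method. Rejecting both nulls "would mean that the relative risk lies in the zone of equivalence".

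The reported outputs are "relative risk, equivalence limits, 90% confidence limits, and TOST p-values of lower margin, upper margin, and overall". The 90% limits imply 0.05 per margin, although no level is stated. IM mock Tables 14.2.1 and 14.2.2 repeat the rule ("Two one-sided tests of significance (TOST) using Farrington-Manning Method and z-statistics, within an 80%-125% criteria") and place a relative risk at or beyond the "Upper Margin of the equivalence limits" in the null. Push SAP 4.4 and push mock Table 14.2.2 carry the same rule.

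Protocol 9.7 asks only that the proportions be comparable by Fisher's exact test, with no margin and no direction. It also calls trough the exposure measure that better represents efficacy. Protocol 1.3 treats 0.3 µg/mL as the effective concentration.

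**The concern.** A trough above the effective concentration is what the treatment is meant to achieve, so a higher proportion above it is better. A proportion cut at a minimum level says nothing about over-exposure, because a trough just above 300 ng/mL counts the same as one many times higher. Over-exposure is addressed by the 125% limit on AUC and by the safety analyses. The upper margin therefore guards against nothing, yet it can withhold the bridge from a route that does better or equally well.

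Trough is a primary objective for IM (IM SAP 2.2.1) and, together with AUC, for push (push SAP 2.2.1). The rule thus bears on a main conclusion of each part.

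**Working it through.** **Stated power.** Protocol 9.8 gives 80% for 20 subjects per administration, argued from clearance and AUC variability. A paired two-one-sided-tests calculation on log AUC (n=20, true ratio 1.00, one AUC per route) gives about 100% at a within-subject CV of 7%, and 86% and 82% at 22% and 23%. The figure is plausible for AUC. No power is stated for the trough test.

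**Inputs.** n=20 per route (IM SAP 3.1; push SAP 3.1); margins 0.80 and 1.25; one-sided 0.05 per margin, implied by the 90% limits; event at or above 300 ng/mL, as in the mock tables; one outcome per subject per route; samples treated as independent, as the SAP does.

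**Test.** With observed proportions p_T (new route) and p_R (infusion) and margin ρ, the restricted estimate x of p_T is the smaller root of

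2x² − [ρ(1+p_R) + 1 + p_T]x + ρ(p_T+p_R) = 0, with y = x/ρ for infusion,

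and z = (p_T − ρp_R) / √{[x(1−x) + ρ²y(1−y)]/n}.

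**IM 20/20, upper margin.** With p_T=1 and ρ=1.25 the roots are 1 and 0.625(1+p_R). For p_R of at least 0.6 the smaller is x=1, so y=0.8. The standard error is √(1.5625×0.16/20) = √0.0125 = 0.1118, and z = (1 − 1.25p_R)/0.1118.

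| Infusion | z | Upper p | Lower p | Both rejected |
|---|---|---|---|---|
| 20/20 | −2.24 | 0.013 | 0.013 | yes |
| 19/20 | −1.68 | 0.047 | 0.007 | yes |
| 18/20 | −1.12 | 0.13 | 0.003 | no |
| 17/20 | −0.56 | 0.29 | 0.002 | no |
| 16/20 | 0.00 | 0.50 | 0.001 | no |

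Over all 190 possible results with IM above infusion (infusion at least 1/20), 1 passes, 155 fail on the upper margin only, and 34 fail the lower margin too. These results are not equally likely; the count only shows the shape of the rule.

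**Chance of passing, independent binomials, n=20 per route.**

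| True infusion / IM | Both margins | Lower only |
|---|---|---|
| 80% / 80% | 2% | 38% |
| 90% / 90% | 23% | 59% |
| 95% / 95% | 58% | 79% |
| 90% / 100% | 39% | 100% |
| 80% / 95% | 8% | 95% |
| 80% / 63% | 0.1% | 4% |

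**Dependence and unit.** If every subject has the same outcome on both routes, the two counts are equal. Because 1/0.80 = 1.25, the two p-values are then identical and the upper margin costs nothing. If troughs are pooled and treated as independent, 40 against 40 (assuming two per subject per route), equal rates of 90% give 66% with both margins and 83% with the lower alone.

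**Agreement with the protocol's test.** At 20/20 against 16/20, the probability that all four failures fall in one named group is C(20,4)/C(40,4) = 4845/91390 = 0.053, so Fisher's two-sided p is 0.11. That shows no significant difference, while the SAP test withholds the bridge at upper p=0.50.

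**Event column.** SAP 4.5 codes below 300 as 1, and the code orders columns by the data with a format that is not shown, so the column used for the relative risk is not fixed. If it is the below-300 column, the roles of the margins reverse. With 10/20 below on IM and 4/20 below on infusion (relative risk 2.5), the 0.80 null is rejected at p=0.006 although IM is worse.

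**The case against.** The case for leaving the rule alone has real force.

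- **The aim is comparability.** Protocol 9.7 and the SAP ask for comparable proportions without a direction, so moving to one margin changes the claim. This stands as a cost. It does not supply a reason for penalising more subjects above an efficacy threshold.
- **Much of the failure is imprecision.** A reader might infer that any better result fails, or that a better route exceeds 1.25. Neither is supported: 20/20 against 19/20 passes, and once the true infusion rate is 80% or more no true relative risk can exceed 1.25. Failure there means 20 subjects cannot exclude a margin that no true value can cross. Equal results of 17/20 fail both margins (p=0.068 each), and a one-sided rule does not cure that.
- **IM may not be better.** A reader might take the 95% against 80% row as a forecast. The infusion figure comes from Study TMB-301 (Protocol 1.3): "With the loading dose, the percentage of subjects below effective concentration and receptor occupancy decreased from" about 50% to about 20%, but at Week 2, with steady state placed at Week 4. The IM rate of 95% is assumed. The only IM figure in the documents is 63% above 0.3 µg/mL, from an arm of eight, and at 63% against 80% the change hardly matters.
- **The outputs are transparent.** The mock tables show both proportions, the interval and separate lower and upper p-values, and the analysis is called primarily descriptive. A reader could see the lower margin met. That limits the harm, but the declared rule would still say no bridge.

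**Conclusion.** The point holds as an unjustified upper margin on a favourable proportion. With 20 subjects per route it usually blocks a result in which the new route does better, and it lowers the chance of passing when the routes are truly equal. Under independence that loss is 36 percentage points at 80% and at 90%, and 21 at 95%. It shrinks with pooled measurements and vanishes at equal rates with full concordance. Real paired data should lie between, since the same subjects receive both routes.

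Infusion rates below 95% are plausible: Protocol 1.3 reports a median Week 25 trough of 0.23 µg/mL in subjects over 85 kg, so at least half of that subgroup were below 0.3.

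The error is conservative: the upper margin can only withhold a bridge and cannot award one to an inferior route. The change should be made, but the documents do not support reading this as a threat to the validity of a positive result, or as a prediction that the bridge will fail because IM is better.

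**What to change.** Before PK data are reviewed, amend IM SAP 4.5 and push SAP 4.4 as follows.

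1. Declare the trough bridge when the relative risk (new route over infusion) of the proportion at or above 300 ng/mL exceeds 0.80 at one-sided 0.05. Equivalently, the lower limit of the two-sided 90% interval, from the same score method, must exceed 0.80.
2. Name at or above 300 ng/mL as the event in the text, and fix that column in the PROC FREQ code. Without this, dropping the upper margin could pass a worse route.
3. Keep reporting the two-sided 90% interval. Label the upper-margin and overall p-values descriptive in IM mock Tables 14.2.1 and 14.2.2 and push mock Table 14.2.2.
4. Keep 80-125% for AUC as the check on over-exposure.

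The cost is SAP, code and mock-table wording. The level of the lower test is unchanged. The trough claim becomes non-inferiority instead of equivalence. Low precision at 20 subjects, the independence assumption for paired data, and whether subjects or pooled measurements are counted remain to be settled separately. Made after the PK data are seen, the same change would look data-driven.

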#### ***4.6. Secondary Efficacy Endpoint***

Assessment of the HIV-1 viral load measurements in HIV-1 infected subjects will be made as a secondary endpoint by comparing the mean viral load ( $\log_{10}$  and copies/ml) at all visits when subjects received an approved IV infusion over 15 minutes to the visits when receiving an IM injection. The comparison is objective, no statistical tests will be performed. Note: Prior to calculating change from Baseline in viral load, the  $\log_{10}$  value of each measurement will be calculated and will be rounded to one decimal point.

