## 9.6 Efficacy

Assessment of the HIV-1 viral loads will be made as a secondary endpoint in HIV-1 infected subjects by comparing the mean viral load at visits when subjects received an IVI over 15 minutes to the weekly visits when receiving an IV push over 30 seconds or IM injections.

Study subjects will be considered virologic failures if:

1. Viremic subjects experience a sustained  $>0.5$  log increase in plasma HIV-1 RNA from baseline  
or
2. A sustained viral load (VL)  $>200$  copies/mL if subject VL was  $<50$  copies/mL at baseline

that cannot be explained by intercurrent illness, a change in adherence to the background regimen, or unanticipated changes to the background regimen that will meet the definition of virologic failure.

Sustained is defined as 2 consecutive viral load determinations at least 2 weeks apart.

Exploratory statistical analyses will explore changes in HIV-1 drug sensitivity/susceptibility to determine relationships with Trogarzo® administration in combination with background ARVs.

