**Listing 16.2.6**  
**Viral Load**

Group	Subject ID	Virologic Failure? 	Visit	Visit Date (Study Day)	Period 	Treatment Date (Study Day)	Viral Load (log 10 cp/mL) 	Chg from Baseline (log 10 cp/mL) 	HIV-1 RNA (cp/mL)
IM HIV Infected	XX-XXX	Y/N	XXXX	YYYY-MM-DD (XX)	XXXX	YYYY-MM-DD (XX)	XX	XX	XX
			XXXX						XX
			XXXX						XX
			XXXX	YYYY-MM-DD (XX)	XXXX	YYYY-MM-DD (XX)	XX	XX	XX
			XXXX						XX
			XXXX						XX
	XX-XXX	Y/N	XXXX	YYYY-MM-DD (XX)	XXXX	YYYY-MM-DD (XX)	XX	XX	XX
			XXXX						XX
	XX-XXX	Y/N	XXXX	YYYY-MM-DD (XX)	XXXX	YYYY-MM-DD (XX)	XX	XX	XX
			XXXX						XX
			XXXX						XX
			XXXX						XX
	XX-XXX	Y/N	XXXX	YYYY-MM-DD (XX)	XXXX	YYYY-MM-DD (XX)	XX	XX	XX
			XXXX						XX

[1] Y = Virologic Failure per protocol: Viremic subjects experience a sustained >0.5 log increase in plasma HIV-1 RNA from baseline. OR A sustained VL>200 copies/mL if subject VL was <50 copies/mL at baseline.

Note: Sustained is defined as two consecutive viral load determinations at least 2 weeks apart.

[2] Period represents the timeframe when the visit took place. NOTE - Since labs are assessed pre-dose, the value of PERIOD in the lab listings will be previous to the value of PERIOD in listings for post-dose assessments.

[3] Last treatment prior to viral load measurement.

[4] \*=below 400 copies/mL; \*\*=below 50 copies/mL. HIV-1 RNA level results below level of quantitation are coded as target detected (TD) or target not detected (TND).

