#### 4.5. Secondary Efficacy Endpoint

Assessment of the HIV-1 viral load measurements in HIV-1 infected subjects will be made as a secondary endpoint by comparing the mean viral load (log10 and copies/ml) at all visits when subjects received an approved IV infusion over 15 minutes to the visits when receiving an IV push over 30 seconds. Note: Prior to calculating change from Baseline in viral load, the log10 value of each measurement will be calculated and will be rounded to one decimal point.

Study subjects will be considered virologic failures if:

1. Viremic subjects experience a sustained >0.5 log increase in plasma HIV-1 RNA from Baseline

or

2. A sustained viral load >200 copies/mL if subject viral load was <50 copies/mL at Baseline

that cannot be explained by intercurrent illness, a change in adherence to the background regimen, or unanticipated changes to the background regimen. Note: Sustained is defined as two consecutive viral load determinations at least 2 weeks apart.

The proportion of subjects who experienced virologic failure at any time during the study will be summarized.

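### Rounding log10 viral load to one decimal before taking change from Baseline can turn the >0.5 log virologic-failure limit into >=0.6 and under-count failures

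*SAP*

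**What the plan says.** The SAP file holds two plans, one for the IM injection portion and one for the IV push portion.

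- **IM SAP 4.6** compares mean viral load between infusion and IM visits, descriptively. A note says that the log10 of each viral load "will be calculated and will be rounded to one decimal point". The note also fixes the order of operations, since this is to be done "Prior to calculating change from Baseline in viral load". The section does not mention virologic failure.
- **IM Listing 16.2.6** has a yes/no failure column beside log10 viral load, log10 change from Baseline and raw copies/mL. Its footnote reads "Y = Virologic Failure per protocol" and gives two criteria. One is "Viremic subjects experience a sustained >0.5 log increase in plasma HIV-1 RNA from baseline". The other applies to baselines below 50 copies/mL and needs a persistent count above 200 copies/mL.
- **IV push SAP 4.5** carries the same note (the log10 "value of each measurement will be calculated and will be rounded to one decimal point"). The same section then sets the limit, "Viremic subjects experience a sustained >0.5 log increase in plasma HIV-1 RNA from Baseline", and says that the proportion of subjects with failure will be summarised.
- **Protocol 9.6** gives the same two criteria with no rounding. It requires persistence: "Sustained is defined as 2 consecutive viral load determinations at least 2 weeks apart". The rise must also not be explained by intercurrent illness, adherence or regimen change.

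Neither SAP defines any log10 change from Baseline other than the rounded one. Neither says whether the failure flag uses rounded or unrounded values.

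**The concern.** The failure limit is strict and has one decimal, and the rounding is to that same decimal. Rounding before subtracting therefore puts many changes exactly on the limit, where a strict inequality fails them all. Whether a given rise counts then depends on where the baseline falls within its rounding interval as well as on the size of the rise.

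Maintenance of virologic control is a stated secondary assessment. The groups are small (about 20 subjects per new route, some of them HIV-uninfected), so a single failure more or less is visible. For a subject with detectable virus at baseline the log criterion is the only one that applies, because the >200 copies/mL criterion is restricted to baselines below 50 copies/mL.

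**Working it through.** The plan gives no figure to reproduce here, and no power or alpha is involved.

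**Inputs.** Each log10 value rounded to 0.1, then subtracted (IM SAP 4.6, IV push SAP 4.5). Limit: rise strictly >0.5 log (Protocol 9.6, IV push SAP 4.5, IM Listing 16.2.6). Entry: viral load <1,000 copies/mL at Screening (Protocol 5.1). Assumption: viremic means a baseline of at least 50 copies/mL; the documents do not define it.

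**Step 1, bounds.** A rounded change r is a multiple of 0.1, so >0.5 means r >= 0.6. Each rounding error is at most 0.05, so the true change lies between r - 0.1 and r + 0.1.
- Flagged (r >= 0.6): true rise above 0.50. There are no false failures in exact arithmetic.
- Not flagged (r <= 0.5): true rise below 0.60. Nothing above 0.60 is missed.

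In fold terms, the limit of 10^0.5 = 3.16 becomes a limit somewhere between 3.16 and 10^0.6 = 3.98, depending on the baseline.

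**Step 2, chance of a flag.** Write the baseline as its rounded value plus u, with u between -0.05 and 0.05. A true rise d is flagged when u + d >= 0.55. If u is uniform (assumption), the chance is (0.05 - (0.55 - d))/0.10 = (d - 0.50)/0.10 for d between 0.50 and 0.60.
- d = 0.51: 10% flagged, 90% missed
- d = 0.53: 30% flagged, 70% missed
- d = 0.55: 50% flagged, 50% missed
- d = 0.59: 90% flagged, 10% missed

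**Step 3, enumeration.** All whole-number pairs with baseline 50 to 999 copies/mL and follow-up up to 5 times baseline, with half-up rounding in exact tenths. Of 407,983 pairs with a true rise above 0.50 and up to 0.60, 204,263 are missed (50.1%). No pair with a true rise of 0.50 or less is flagged. The smallest flagged rise is 0.5002 and the largest unflagged is 0.5999.

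| True rise (log10) | Missed |
|---|---|
| 0.50-0.52 | 90% |
| 0.52-0.54 | 72% |
| 0.54-0.56 | 55% |
| 0.56-0.58 | 32% |
| 0.58-0.60 | 10% |

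**Step 4, examples.**
- 60 to 215 copies/mL: 2.332 - 1.778 = +0.554; rounded 2.3 - 1.8 = 0.5, missed.
- 70 to 240 copies/mL: 2.380 - 1.845 = +0.535; rounded 2.4 - 1.8 = 0.6, flagged.
- 70 to 222 copies/mL: 2.346 - 1.845 = +0.501; rounded 2.3 - 1.8 = 0.5, missed.

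The first rise is larger than the second, yet only the second counts.

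**Step 5, two consecutive values.** Both changes share one rounded baseline. If both rises fall independently and uniformly in the band, the chance that both are flagged is the mean of p squared for p uniform on 0 to 1, which is 1/3. About 67% of such sustained rises are then missed. If the two follow-up values are equal, or the second rise exceeds 0.60, the chance is the same as for one value.

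**Step 6, programming.** In ordinary floating point 2.2 - 1.7 evaluates to 0.5000000000000002 and passes a >0.5 test. In the enumeration this falsely flags 183 of 324,074 pairs with a true rise of 0.40 to 0.50. That is a coding trap created by values sitting on the limit, not part of the SAP's rule.

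**The case against.** The strongest reply is that the rounding note may have nothing to do with the failure flag. In the IM SAP the note sits in a section about mean viral load that never mentions failure, and the IM listing defines its flag by reference to the protocol, which does not round. A programmer could properly use unrounded values. This stands: for the IM portion the text is ambiguous, not demonstrably wrong. It has less force for the IV push SAP, where the note, the limit and the summarised proportion share one section. Nor does it remove the need for clarification. If the flag uses unrounded values, the listing can show a failure beside a printed change of 0.5, and the SAP does not say which governs.

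The small reach also stands. Only viremic subjects use the log criterion, the number of such subjects is not given, and the listings show raw copies/mL, so quantified values can be rechecked.

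A reader might go further and infer three things that the documents do not support.
- That every rise between 0.50 and 0.60 is lost. About half are, and the share falls from 90% at 0.51 to 10% at 0.59.
- That the rounding favours IM or IV push. The same rounding applies at infusion, push and IM visits. The planned comparison by route is of mean viral load, and no contrast of failure rates between routes is planned.
- That requiring two values always makes the loss larger. It does so only when both rises fall in the band and differ.

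**Conclusion.** The point holds conditionally. Followed as written, the rounding gives the only log10 change that either SAP defines. If that change feeds the >0.5 log rule, the limit becomes >=0.6, which departs from the protocol's unrounded rule and depends on the baseline's digits. About half of single true rises between 0.50 and 0.60 log would be missed, and in exact arithmetic none at or below 0.50 would be flagged, so any error is an under-count of failure overall.

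The percentages assume a uniform baseline position within the rounding interval, or equal weight on the enumerated pairs, with viremic taken as 50 copies/mL or more. They describe rises inside a narrow band and do not predict how many subjects will be affected. The confirmed-failure figure of about 67% needs the further assumption in Step 5. The practical effect is likely to be small, but the ambiguity is avoidable.

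**What to change.** In IM SAP 4.6 and IV push SAP 4.5, delete the rounding clause. In its place, state that change from Baseline in viral load and virologic-failure status are both calculated from unrounded log10 values, and that rounding is for display only. Repeat this in the footnotes of the viral load listings (IM Listing 16.2.6, IV push Listing 16.2.5.3), so that a failure printed beside a displayed change of 0.5 is understood.

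With unrounded values, the enumeration in Step 3 gives no missed rises and no false flags, and the classification matches the protocol. The cost is one sentence in each SAP and a footnote in each listing. It needs no new data, no change to the protocol and no change to any visit.
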